	3 DATA PROCESSING	
	ACCESS TO DATA	
9	MONITORING, AUDIT & INSPECTION	.13
10	ETHICAL AND REGULATORY CONSIDERATIONS	.13
10.1 10.2		
10.2		
10.0		

10.4	PROTOCOL COMPLIANCE AND SERIOUS BREACHES	15
10.5	DATA PROTECTION AND DATA SUBJECT CONFIDENTIALITY	15
10.6	INDEMNITY	15
10.7	ACCESS TO THE FINAL PROJECT DATASET	15
11 DI	SSEMINATION POLICY	16
12. REFE	RENCES	17

LIST OF ABBREVIATIONS

CI	Chief Investigator
GCP	Good Clinical Practice
NHS R&D	National Health Service Research & Development
PI	Principal Investigator
PIC	Participant Identification Centre
PIS	Participant Information Sheet
REC	Research Ethics Committee
SOP	Standard Operating Procedure

PROJECT SUMMARY

Project Title	Getting the bloods to the labora to improve the blood culture pa antimicrobial stewardship.	atory: developing interventions athway for patient safety and
Project Design	Cross-sectional study involving	analysis of routine NHS data
Planned Sample Size	No sample size was calculated all eligible participants	as data will be extracted for
Follow up duration	At time of extraction data will be extracted for the previous 12 months	
Planned Project Period	Jan 2023- June 2025	
	Objectives	Outcome Measures
Primary	To identify rate of occurrence and situational factors that affect whether blood culture sampling occurs, when broad-spectrum antibiotics for intravenous administration are prescribed within 24 hours of patient admission from emergency departments (ED).	% of participants where a blood culture sample was ordered
Secondary	To identify factors impacting on quality indicators e.g., number of sets, contamination, time to microbiology lab analyser; whether blood culture sampling occurs prior to administration of antibiotic. To conduct a secondary analysis to assess extent to which availability of blood samples was associated with changes to antibiotic choice at antibiotic review.	Adjusted odds ratios from logistic regression models

FUNDING AND SUPPORT IN KIND

FUNDER(S) (Names and contact details of ALL organisations providing funding and/or support in kind for this project)	FINANCIAL AND NON FINANCIALSUPPORT GIVEN
National Institute for Health Research (NIHR156452)	Financial support (£752,059.85)

ROLE OF PROJECT SPONSOR

The sponsor of this research is the University of Leicester. The University of Leicester is registered as a research sponsor with the Department of Health and routinely takes responsibility as sponsor for research activities within the NHS.

DATA FLOW DIAGRAM

1 BACKGROUND

Inappropriate antibiotic use contributes to the growing problem of antimicrobial resistance. In England in 2020, 55,000 patients were affected by antibiotic-resistant infections putting them at risk of poor outcomes and death (1). Evidence shows that resistance results from the overuse of broad-spectrum antibiotics, and prolonged courses of antibiotics, but the use of antibiotics, particularly broad-spectrum antibiotics, continues to increase in hospitals in England (2). As well as the harm posed to patients by the rise of antimicrobial resistance, increasing resistance poses a threat to the system in terms of increased costs and care burden.

Currently, in England, the rapid administration of broad-spectrum antibiotics is recommended for acutely unwell patients with sepsis (3). Additionally. broad-spectrum antibiotics are often initiated 'just in case', for suspected infection, to manage risk (4). In these circumstances, collecting and analysing timely and good quality blood cultures are important to inform the review and potential revision of the initial prescribing decision to an antibiotic that specifically targets the patients infection (5 6,7). The rapid identification of pathogens from blood cultures is known to play a role in reducing individual an population mortality from severe infection and sepsis (8, 9,10).

Performing blood cultures reliably has been identified as a key quality indicator for appropriate antibiotic use in hospitalised adults with suspected severe infection (11), and the presence of microbiology results for all patients identified as one of three priority factors with the greatest influence on optimising antibiotic use in hospitals (12).

Despite the known importance of the knowledge that blood analysis can realise, we also know that the process of blood collection and transportation to the microbiology laboratory can reduce the quality and utility of microbiology results (13). For example, an insufficient volume of blood taken for testing, the contamination of blood samples, and delays in transport are all factors that can substantially and adversely affect the diagnostic value of samples. (14).

Furthermore, an additional issue of concern is that, despite the importance of blood cultures for patient management and antimicrobial stewardship, around half of hospital patients do not have blood samples taken at all when antibiotics are started (15-19).

2 RATIONALE

Whilst we have ample evidence to indicate that blood sampling procedures and processes do not always meet the standards of best practice, we have little knowledge of why that occurs. We need to better understand the behavioural, social, and organisational factors that contribute to poor quality blood sampling in acute care.

There is a pressing need for novel theory-based research and intervention development to optimise the pre-analytic blood culture pathway to bolster both patient safety and effective antimicrobial stewardship. Although interventions have been developed to address problems in acute pathways, these have tended to focus on clinical and technical issues, as opposed to social, behavioural and other factors (14, 20, 21). The blood culture pathway is complex and involves many actors and the timely co-ordination of effort to get the blood to the lab. Blood

sampling practices are potentially underpinned by a complex range of behavioural, cultural and systems factors (22). Recommendations have been made for the need for multi-model approaches to improve blood culture collection practices, based on research using mixed-methods, to generate a holistic knowledge of pathways and thus mitigate barriers to quality improvement and stewardship. (23).

Following on from our previous theory-driven research into overuse of broad-spectrum antibiotics in acute medical patients (4, 24), we draw on theories of individual and collective behaviour to identify the behavioural, social and organisational influences on the reliability and quality of blood culture sampling in acute care, and to develop interventions that will be implementable across diverse health care settings.

As a whole the study used mixed methods. This protocol refers to Part 1 a which involves analysis of routine hospital data.

3 OBJECTIVES AND OUTCOME MEASURES/ENDPOINTS

3.1 Primary objective

To identify rate of occurrence and situational factors that affect whether blood culture sampling occurs, when broad-spectrum antibiotics for intravenous administration are prescribed within 24 hours of patient admission from emergency departments (ED).

3.2 Secondary objectives

To identify factors impacting on quality indicators e.g., number of sets, contamination, time to microbiology lab analyser; whether blood culture sampling occurs prior to administration of antibiotic.

To conduct a secondary analysis to assess extent to which availability of blood samples was associated with changes to antibiotic choice at antibiotic review.

3.3 Outcome measures/endpoints

3.4 Primary endpoint/outcome

Primary outcome measure is occurrence of blood culture sampling. In line with Shallcross (2016) (18) we define blood culture sampling as a request for a blood culture recorded in hospital records within 48 hours of patient arrival at ED (Y/N)

3.5 Secondary endpoints/outcomes

Quality indicators (e.g., number of sets, contamination, time to microbiology lab analyser; whether blood culture sampling occurs prior to administration of antibiotic.)

Changes to antibiotic choice at antibiotic review.

4 STUDY DESIGN

Study design: Cross-sectional study involving analysis of routine NHS data

Combined Protocol V3.0 22/07/24

Sample: All patients >18 years admitted to each trust, receiving broad-spectrum antibiotics for intravenous administration within 24 hours of admission, over a retrospective 12 month period (e.g. March 2023-February 2024).

Data sources: One hospital, with the main ED, will be selected from each trust. Data will be extracted from hospital electronic health records and electronic microbiology records. We will develop a standard schedule detailing the data points required and providing definitions. This will be discussed with the informatics team in each site to ensure comparable data can be provided. A data-sharing agreement will be established with each site.

Data will be fully anonymised within the trusts prior to transfer, by the nominated member of staff in the trust responsible for extracting and compiling the data. Identifying information e.g. date of birth and postcode will be substituted with higher level information e.g. age and Super Output Area. Primary data will be provided, trusts will Zip and encrypt data using 7-Zip software, and transfer using the University's secure Filedrop facility - https://filedrop.le.ac.uk/

We will incorporate internal checks of data-completeness (e.g. instances of patients with a blood culture result but no data on the time sample was ordered). Blood culture order time may not correlate with collection time. We will conduct a prospective data quality check, involving the use of stickers or audit forms to capture a manual record of actual blood culture sampling time. This will be checked against blood sample order time, and time of first dose of antibiotic, to assess the alignment between order time and collection time, and whether collection time precedes antibiotic administration, as a validation check of our use of blood culture sample order time as the primary outcome measure of blood culture sampling. Anonymised audit data will be transferred to the University of Leicester for and compiled for cross-site analysis.

5 INCLUSION/EXCLUSION CRITERIA

5.1 Inclusion criteria

- adults (>18 years)
- admitted to hospital through emergency routes between 01/03/2023 and 29/02/2024
- prescribed broad-spectrum antibiotics for intravenous administration within 24 hours of admission

5.2 Exclusion criteria

- individuals under the age of 18
- individuals admitted to hospital via through elective routes or not admitted to hospital between 01/03/2023 and 31/02/2024
- individuals not prescribed broad-spectrum antibiotics for intravenous administration within 24 hours of admission

6 STUDY PROCEDURES

6.1 Informed consent

We will be obtaining anonymised data sets from trusts in line with their Privacy Notice, therefore there is no need for consent as there will be no breach of the common law duty of confidence.

6.2 Definition of End of Study

When all analyses have been completed in line with the Statistical Analysis Plan, no later than the End Date approved by the Ethics Committee.

6.3 Source Data

Analysis will identify situational/contextual predictors of reliable blood culture sampling. We have specified a minimum set of measures, identified in agreement with the three participating hospitals based on routine data that is collected and could be made available from all three hospitals. This will be developed into a fully-specified data extraction schedule with input from our expert advisory group (e.g. listing the broad spectrum antibiotic that are of interest), tailored for each hospital to reflect variations in the way their data are coded. This will include the following measures:

- Date & time of arrival in ED/admissions unit
- Antibiotics patient is already taking prior to admission where applicable
- Location antibiotic prescribed (ED, AMU etc)
- Type of antibiotic prescribed
- · Date and time antibiotic prescribed
- Dates and times of antibiotic administration
- Documented microbiology results
- Changes to antibiotic schedule
- Patient demographics (IMD based on postcode, year of birth, ethnicity, gender)
- Patient severity (NEWS score)
- Recorded diagnosis at admission and at discharge

Where available we will also collect data on quality indicators as secondary outcomes:

e.g., number of sets of blood culture bottles filled (guidelines recommend 2 sets of two bottles), contamination of sample, time to microbiology lab analyser

7 STATISTICS AND DATA ANALYSIS

Data analysis:

Descriptive statistics will be used to summarise the frequency and distribution of timing of blood culture ordering. We will also produce histograms or box plots to visualise the distribution of these measures. Logistic regression will be used to assess covariates associated with the probability of blood culture being ordered within 48 hours of admission (binary yes/no outcome). Relevant covariates to be assessed include situational/contextual factors, patients demographics, and patient outcomes.

To identify factors impacting on quality indicators e.g., number of sets, contamination, time to microbiology lab analyser; whether blood culture sampling occurs prior to administration of antibiotic, appropriate methods will be used depending on the data type of the quality indicator. Continuous variables will be assessed via linear regression, and binary quality indicators by logistic regression.

A final analysis to investigate the extent to which availability of blood samples was associated with changes to antibiotic choice at antibiotic review will be assessed again using logistic regression (with yes/no antibiotic changed as the dependent variable, and yes/no blood sample available as the independent.

All models will be fully adjusted for covariates such as patient age, and will be mixed effects to account for the clustering effect of hospital, as data is being drawn from three sites. We will conduct sensitivity analyses to test the robustness of our results to different assumptions and model specifications. This will help to assess the reliability of our findings and identify potential sources of bias. We will carefully consider the strengths and limitations of each method and choose the most appropriate approach for each research question.

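### Part 1a lists patient outcomes as covariates in the model for blood culture ordering, although outcomes follow the culture decision and cannot be factors that affect it

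*Protocol*

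**What the plan says.** All references are to the protocol, Part 1a.

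- **Objective (section 3.1):** "To identify rate of occurrence and situational factors that affect whether blood culture sampling occurs". Section 6.3 repeats the aim: "Analysis will identify situational/contextual predictors of reliable blood culture sampling".
- **Dependent variable (sections 3.4 and 7):** a recorded request for a blood culture within 48 hours, yes or no, analysed by logistic regression.
- **Covariates (section 7, directly after the regression sentence):** "Relevant covariates to be assessed include situational/contextual factors, patients demographics, and patient outcomes".
- **Adjustment rule (section 7):** "All models will be fully adjusted for covariates such as patient age, and will be mixed effects to account for the clustering effect of hospital".
- **Data collected (section 6.3):** the minimum data set includes the NEWS score and "Recorded diagnosis at admission and at discharge", together with microbiology results and changes to the antibiotic schedule. It lists no death, length of stay or intensive care admission.

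Part 1a does not define the term patient outcomes. Nothing limits it to variables known before the culture, or to a separate analysis.

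**The concern.** A predictor of a decision has to exist when the decision is made. The dependent variable is an order placed early in the stay, whereas a patient outcome is observed later. The protocol also gives a causal direction of its own. Section 1 (Background) says that rapid identification of pathogens from blood cultures helps to lower mortality. The last analysis in section 7 models a change of antibiotic as dependent on whether a blood sample was available. In both places, what happens after the culture is treated as a consequence. In the primary model, the class of patient outcomes is placed on the predictor side.

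If a later outcome depends both on the culture and on a predictor, putting it in the model opens a non-causal path between that predictor and the culture. A real predictor can then look weaker or stronger than it is, and a factor with no effect can appear to have one. Adjusted odds ratios are named as an outcome measure in the project summary, and the findings are meant to feed intervention design and policy advice.

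**Working it through.** Part 1a gives no sample size, power or effect size, so there is no figure to reproduce. The check asks how far an odds ratio (OR) moves when a later outcome is added. **Every numerical input below is an assumption; none comes from the protocol.**

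**Set-up.** Let Y be culture ordered, H high severity and D a later outcome, all binary.

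- logit P(Y) = a + b·H, with b = 0.69, so the true severity OR is e^0.69 = 1.99
- logit P(D) = c + s·H + k·Y, with c = −2

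With a = −0.3 and 30% high severity, the culture rate is 0.7 × 0.426 + 0.3 × 0.596 = 0.48. This is close to the roughly one half in the Background.

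**Formula.** By Bayes' rule,

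logit P(Y | H, D) = a + b·H + k·D + ln[(1 + e^(c+sH)) / (1 + e^(c+sH+k))].

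The OR for H after adjustment for D is therefore e^b × R, where

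R = [(1 + e^(c+s)) / (1 + e^c)] ÷ [(1 + e^(c+s+k)) / (1 + e^(c+k))].

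**When there is no bias.** If k = 0 (culture does not affect the outcome) or s = 0 (the predictor does not relate to the outcome except through the culture), then R = 1 exactly. If s and k are both positive, R < 1. If s is positive and k negative, R > 1.

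**Culture raises the outcome**

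| s | k | R | Severity OR (true 1.99) |
|---|---|---|---|
| 1.0 | 1.0 | 1.2048 / 1.4621 = 0.824 | 1.64 |
| 0.7 | 1.5 | 1.1208 / 1.3827 = 0.811 | 1.62 |
| 1.2 | 1.2 | 1.2766 / 1.7193 = 0.743 | 1.48 |
| 1.2 | 2.0 | 1.2766 / 2.1601 = 0.591 | 1.18 |

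For a factor with no effect on ordering (b = 0), the adjusted OR is R itself: 0.82 for (s, k) = (1, 1), 0.73 for (1, 1.5) and 0.61 for (1.5, 1.5).

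**Culture mildly protects against the outcome**

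| s | k | R | Severity OR (true 1.99) |
|---|---|---|---|
| 0.7 | −0.2 | 1.1208 / 1.1011 = 1.018 | 2.03 |
| 1.0 | −0.2 | 1.2048 / 1.1714 = 1.029 | 2.05 |
| 1.0 | −0.5 | 1.2048 / 1.1303 = 1.066 | 2.13 |

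**Second check by simulation** (400,000 patients per scenario; situational factor with true OR 0.70, severity with true OR 1.50 per SD).

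- Outcome left out: 0.69 to 0.71 and about 1.50, so the true values are recovered.
- Protective culture (OR on the outcome 0.8 to 0.4; factor's OR on the outcome 1.5 to 2.5): the situational OR becomes 0.72 to 0.79.
- Culture raises the outcome (OR 2 to 8; factor's OR on the outcome 0.5 or 2): the situational OR becomes 0.51 to 0.96.
- Factor unrelated to the outcome: its OR stays at about 0.70.
- No effect of culture on the outcome, but one unmeasured cause shared by both: adding the outcome moves the situational OR from 0.73 to 0.68 and the severity OR from 1.46 to 1.36.

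**The case against.** **It may be a slip of wording.** Situational factors, demographics and patient outcomes leave no obvious place for NEWS or admission diagnosis, which section 6.3 collects, and no clear outcome such as death is on that list. The phrase may have been meant for severity or diagnosis. That is plausible, but the sentence then names the wrong class and still needs correcting.

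**Assessing covariates need not mean adjusting for them.** The adjustment sentence gives only age as an example, and section 6.2 refers to a statistical analysis plan that may fix the final set. This softens the point. However, the covariate sentence follows directly from the regression sentence, full adjustment is promised for all models, and a plan that followed this text would carry the error forward. The promised sensitivity analyses do not say that outcomes will be removed.

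**Stronger readings that the documents do not support.** A reader might infer that every adjusted association is distorted. That is not so: R = 1 when the predictor is unrelated to the outcome, or when the culture does not affect it and no unmeasured cause is shared. A reader might also take 1.2 or 0.61 as the expected damage. Those values need a culture that strongly raises the outcome, whereas the one patient outcome that the Background links to cultures, mortality, runs the other way and gives small shifts. Finally, a reader might infer that section 7 makes discharge diagnosis or microbiology results covariates. It names neither; section 6.3 only lists them as collected.

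**Conclusion.** The concern holds: the covariate rule is wrong as written, and this is not a detail merely left to the analysis plan. Outcomes follow the order, and the protocol itself treats them as partly a consequence of cultures, so they do not belong in a model of what affects ordering.

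The possibility of bias is firm; its amount is not. It reaches only predictors that relate to the outcome, or cases where culture and outcome share an unmeasured cause. Its direction depends on whether the culture raises or lowers the outcome. Under the assumed values, a severity odds ratio of 2.0 becomes about 1.2 to 1.6 in the first case and about 2.0 to 2.1 in the second. These figures illustrate the mechanism and do not forecast this study's error. The correction should be made before the analysis because it concerns the primary objective and is cheap. Data collection is unaffected.

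**What to change.** In Part 1a, section 7:

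1. Delete patient outcomes from the covariate list.
2. State that covariates in the ordering model are limited to variables fixed before the culture decision, for example arrival time, demographics, first recorded NEWS, prior antibiotics and admission diagnosis. Use prescribing location only where it precedes the order. The limit should be the culture decision, not the antibiotic prescription, because an order may come before the prescription.
3. State that later items in the data set (discharge diagnosis, microbiology results, changes to the antibiotic schedule) are not covariates in that model.
4. If patient outcomes are of interest, define them and analyse them separately as dependent variables.

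If the phrase was meant to cover severity or admission diagnosis, name those variables instead. The cost is a sentence or two of text, carried into the statistical analysis plan. No new data are needed.

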4. RESEARCH QUESTION/AIM(S)

As a whole, i-SAMPLE is designed to understand [Part 1] and improve [Part 2], through embedded co-design and evaluation, the blood culture pathway in acute settings. The overall aims of the study are:

- to ensure patients receive the best infection specific antibiotic at the earliest stage of their treatment
- to decrease the overuse of antibiotics which causes antimicrobial resistance

To understand the pathway, we will undertake

- A quantitative analysis of routine hospital data to see when samples are taken and cultures are done, and how that affects antibiotic prescribing: Part 1a.
- A Survey of healthcare professionals' attitudes and beliefs about blood culture: Part 1b.
- Observations of, and interviews with staff who are engaged with the blood culture pathway: Part 1c

In parallel, to improve the pathway, the knowledge gained from Part 1 will be fed into, and support a co-design process, Part 2. Part 2 is intended to map out the factors that affect the blood culture pathway for good or ill, and to define/represent a detailed archetypical blood culture pathway with the aim of using that to develop, pilot and evaluate interventions to improve the pathway.

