5.2.2 Sampling

Site Sampling

Part 1c and Part 2 will take place in three trusts which have been sampled for diversity, University Hospitals Leicester, University College London Hospitals, and Kettering General Hospital NHS Foundation Trust. These trusts serve populations with diverse health needs, ethnicity, and socio-economic status, and are located in different geographical regions.

The trusts vary in antibiotic use (total antibiotic prescribing, and prescribing from the 'Watch' and 'Reserve' WHO AWaRe categories, defined daily doses per 1000 admissions) compared to the England average (51). The trusts use different electronic patient record systems and have differing levels of digital maturity. They include trusts with in-hospital, and outsourced, microbiology laboratory services.

Within-site (Participant) sampling

Part 1c - Interviews: Purposive Sampling

 Hospital staff will be identified during the observation period. Purposive sampling will be undertaken whereby individuals who have been identified during the observations as being key decision-makers/staff with key roles along the pathway will be approached by the site lead, or directly by the researcher if they have already engaged with the researcher during observations, to see if they would be interested in taking part. This will include junior doctors and other staff responsible for requesting and taking blood samples, as well as other key staff along the pathway including microbiology staff. Part 2a - Co-design Workshops: Purposive and snowball sampling

Patients

• Potential patient participants will be recruited from each of the hospitals' PPI groups to include patients with experience of the acute care pathway.

Healthcare staff

• Hospital staff will be recruited through purposive snowball sampling with support from the local clinical and junior doctor lead in each trust. Staff will be approached by the site lead and provided with a copy of the study information leaflet.

Part 2c – Evaluation Focus groups and interviews: Purposive sampling

Healthcare staff

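### The final Part 1a analysis models any antibiotic change as yes/no, so its odds ratio cannot show the direction of change that the rationale and aims turn on

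*Protocol*

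**What the plan says.** The Part 1a protocol specifies this analysis in three places, and none of them gives a direction.

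- Section 3.2 sets the secondary objective: to "assess extent to which availability of blood samples was associated with changes to antibiotic choice at antibiotic review".
- Section 3.5 names the outcome as "Changes to antibiotic choice at antibiotic review", without categories.
- Section 7 fixes the model as logistic regression, "with yes/no antibiotic changed as the dependent variable, and yes/no blood sample available as the independent".

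The reasons given for the work do have a direction. Section 1 of Part 1a says that cultures matter because they inform "potential revision of the initial prescribing decision to an antibiotic that specifically targets the patients infection". Section 4 of the Part 1c/2 protocol states two aims for the study as a whole: "to ensure patients receive the best infection specific antibiotic at the earliest stage of their treatment" and "to decrease the overuse of antibiotics which causes antimicrobial resistance".

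The data to describe direction are already in the minimum set. Section 6.3 of Part 1a lists the type of antibiotic prescribed, changes to the antibiotic schedule, dates and times of administration, and documented microbiology results.

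**The concern.** Every patient in the cohort enters on an intravenous broad-spectrum prescription (Part 1a, section 5.1). From that starting point a change of antibiotic can go several ways. The drug may be replaced by a narrower agent, replaced by a broader one, swapped for one of similar spectrum, or stopped. The planned outcome has one value for all of these.

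This is the only model in Part 1a that links blood cultures to what happens to prescribing. If it returns an odds ratio near 1, a reader cannot tell whether cultures made no difference or whether changes in opposite directions offset each other. If it returns an odds ratio above 1, a reader cannot tell which kind of change became more common. Adjustment for covariates and a larger dataset do not help, because the information is lost when the outcome is coded.

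The coding is written into the protocol itself. The sensitivity analyses promised in section 7 are generic and commit to no directional outcome.

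**Working it through.** **Inputs.** For Part 1a the protocol states no sample size, power, significance level or event rates, so there is no figure of its own to reproduce. All rates below are assumptions chosen to show how the outcome behaves. They are not estimates.

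**Formula.** Unadjusted odds ratio, with a sample against without: OR = [p1/(1 − p1)] / [p0/(1 − p0)].

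**Assumed rates without a sample.** Narrowed 15%, broadened 15%, other change 10%. Any change = 15 + 15 + 10 = 40%.

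**Four assumed patterns with a sample** (other change held at 10%):

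| Pattern | Narrowed | Broadened | Any change | OR any | OR narrowing | OR broadening |
|---|---|---|---|---|---|---|
| A: narrowing up, broadening down | 25% | 5% | 40% | 1.00 | 1.89 | 0.30 |
| B: narrowing down, broadening up | 5% | 25% | 40% | 1.00 | 0.30 | 1.89 |
| C: narrowing up only | 25% | 15% | 50% | 1.50 | 1.89 | 1.00 |
| D: broadening up only | 15% | 25% | 50% | 1.50 | 1.00 | 1.89 |

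The arithmetic:

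- 25% against 15%: (0.25/0.75)/(0.15/0.85) = 1.89
- 5% against 15%: (0.05/0.95)/(0.15/0.85) = 0.30
- 50% against 40%: (0.50/0.50)/(0.40/0.60) = 1.50
- 40% against 40%: 1.00

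**Second set of assumed rates.** With a sample, 30% narrowed and 10% broadened; without, 20% and 20%. Any change is 40% in both groups, so the OR is 1.00. For narrowing the OR is (0.30/0.70)/(0.20/0.80) = 1.71. For broadening it is (0.10/0.90)/(0.20/0.80) = 0.44.

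**Reading.** The planned outcome gives A and B the same answer, and C and D the same answer, although prescribing moves in opposite directions within each pair. Patterns C and D show that exact cancellation is not needed: a plainly positive odds ratio is just as silent about direction. Two directional outcomes separate all four patterns.

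**The case against.** The strongest reply is that the plan does what it says. The objective in section 3.2 asks whether sample availability is associated with changes, section 3.5 repeats this, and section 7 models it. That stands: outcome and objective do not contradict each other. The aims about infection-specific treatment and overuse belong to the whole study and are stated in the Part 1c/2 protocol, while the background sentence in Part 1a is motivation and does not define an endpoint. The gap is therefore between the outcome and the purpose it serves.

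A second reply is that detail may sit elsewhere. Section 6.2 refers to a statistical analysis plan, which is not at hand, and sections 6.3 and 8.1.1 promise a data schedule with definitions. A breakdown could appear there, and nothing in the protocol prevents it. But the protocol already fixes the dependent variable as a single yes/no, so the addition should be made where that is fixed.

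Some stronger readings are tempting, and the documents do not support them:

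- **Narrowing is benefit and broadening is harm.** The documents speak of targeting the infection. A culture may show an organism that the first drug does not cover, and a change to a broader or different agent is then also targeting. Only the overuse aim favours narrowing as such.
- **De-escalation should replace the planned outcome.** That would score culture-directed broadening as failure. If it were based on the first change made, it would also drop the link to antibiotic review and could count changes made before any result was known.
- **An odds ratio above 1 could arise because sicker patients are both cultured and escalated more often.** No passage says so. NEWS score and diagnosis are collected and the models are to be fully adjusted, although age is the only covariate that section 7 names. The point here does not depend on this mechanism.
- **A directional outcome would show that cultures led to better-targeted treatment.** The design is observational and the protocol itself speaks of association.

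**Conclusion.** The point holds in a limited form. The any-change outcome answers the secondary objective as worded, but its odds ratio carries no information on the direction of change. Direction is what the Part 1a rationale and the overall study aims turn on. The size cannot be given from the documents, which state no rates. Under the assumed rates, odds ratios of 1.89 and 0.30 for the two directions sit behind a pooled value of 1.00, and a pooled value of 1.50 fits a rise in either direction equally well. That the pooled outcome cannot separate directions follows from its coding and does not depend on those rates; how much this matters in practice depends on the real mix of changes, which is unknown. This is a secondary analysis and the remedy adds to the planned model, so the change is worth making but does not touch the primary outcome.

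**What to change.** Keep the planned any-change model. In sections 3.5 and 7 of the Part 1a protocol, add the following.

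1. A prespecified classification of the change at antibiotic review: narrowed or stopped, broadened, other switch, no change. Build it from the antibiotic type and schedule-change items in section 6.3, using a spectrum table agreed with the expert advisory group before analysis. The AWaRe categories, which section 5.2.2 of the Part 1c/2 protocol uses to describe trusts ("prescribing from the 'Watch' and 'Reserve' WHO AWaRe categories"), are one possible basis. They are not cited there as a patient-level spectrum ranking, so conventions are needed for some switches.
2. Separate logistic models for narrowing or stopping and for broadening, or one multinomial model, with the same adjustment and the same handling of hospital as the planned model.
3. Where a culture result exists, a description of the change against that result.
4. A statement that results are associations and that broadening is not by itself labelled as harm.

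The cost is one coding table, with conventions and some mapping because coding differs between the three hospitals, and one or two extra models. No new data items are needed beyond those section 6.3 already lists.
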